8.2 Randomization

The randomization procedure that will be implemented for this study will be a block-stratified technique [REDACTED]

[REDACTED]. The randomization will be computer generated by a statistician independent of the study team. Block stratification will ensure there is an adequate statistical power for demonstrating the effectiveness [REDACTED]

[REDACTED]. Accordingly, approximately 120 subjects will be randomized to treatment and 60 subjects to control. [REDACTED]

[REDACTED] All subjects in the control/delayed-treatment group (60 subjects) will receive treatment at their Week 12 [REDACTED]

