8.4 Statistical analyses

Effectiveness and safety endpoints are provided in [Sections 2.2.1 to 2.2.4](#).

The sponsor will finalize the SAP prior to database lock. Deviations from the analyses outlined in this protocol will be documented in the SAP within a section discussing changes to the planned analyses.

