9.9 Investigator compliance

The investigator will conduct the study in compliance with the protocol provided by the sponsor and in accordance with all relevant regulatory guidelines and requirements.

Modifications to the protocol should not be made without the agreement of the investigator and sponsor. The sponsor will submit all protocol modifications to the appropriate regulatory authority in accordance with applicable regulations. All protocol modifications require written IEC/IRB approval/favorable opinion, except in the case of an immediate hazard to subjects.

If an immediate deviation from the protocol is required to eliminate an immediate hazard to subjects, the investigator must contact the sponsor, if possible, to discuss the planned course of action. The investigator must thoroughly document any departure from the protocol and submit appropriate documentation to the sponsor without delay.

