7.1.1 Primary Effectiveness Endpoint

The primary effectiveness endpoint, the proportion of responders, subjects with \geq 1-grade improvement [REDACTED] on the MJAS from baseline to Week 12 will be summarized as counts and percentages for the treatment and control groups.

Two hypothesis tests will be performed for the primary endpoint, in a sequential order. The first hypothesis is to demonstrate at least 50% of treated subjects are responders and the second hypothesis is to compare the treatment group with the control group. Each hypothesis test is a one-sided test at a significance level of 0.025.

[figure not shown]
Hypothesis test 1:

[figure not shown]
$$H_{01}: P_{\text{treatment}} \leq 50\% \quad H_{11}: P_{\text{treatment}} > 50\%$$

Hypothesis test 2:

$$H_{02}: P_{\text{treatment}} \leq P_{\text{control}} \quad H_{12}: P_{\text{treatment}} > P_{\text{control}}$$

For primary hypothesis testing of at least 50% of treated subjects are responders (H_{01} versus H_{11}), the binomial test will be utilized. For primary testing of statistical superiority of treatment over control (H_{02} versus H_{12}), the Fisher's exact test will be used.

[figure not shown]

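### Randomisation is stratified but the primary between-arm test ignores the strata; a stratified exact test and risk difference would be a cheap, small and conditional improvement

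*SAP*

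**What the plan says.** Protocol 8.2: "The randomization procedure that will be implemented for this study will be a block-stratified technique". The stratification factors are blacked out. The same section gives a purpose, "Block stratification will ensure there is an adequate statistical power for demonstrating the effectiveness", with the end of the sentence redacted, and the arm sizes: "approximately 120 subjects will be randomized to treatment and 60 subjects to control".

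SAP 7.1.1: "Two hypothesis tests will be performed for the primary endpoint, in a sequential order". H01 (more than 50% responders in the treated arm) comes first, by a binomial test. H02 (treated rate above control rate) comes second, and for it "the Fisher's exact test will be used". On level: "Each hypothesis test is a one-sided test at a significance level of 0.025". Protocol 8.4.1.1 names the same tests, so the two documents agree.

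The visible text on the primary endpoint mentions neither strata nor a between-arm effect estimate with an interval. Text next to it is redacted. The protocol's abbreviation list includes odds ratio, and the SAP's references cover multiply imputed categorical data and confidence intervals for proportions. A supportive adjusted analysis or an interval may therefore exist out of sight. The primary test itself is named in a complete sentence in both documents.

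**The concern.** If the randomisation factors predict response, a pooled 2×2 test leaves between-stratum variation in the noise. Fisher's test is already conservative at these arm sizes, and pooling over prognostic strata makes it more so. The protocol ties stratification to power, yet the named test makes no use of the strata.

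Two things could be lost: some probability of passing H02, and some precision in the estimated difference in responder rates. The first matters only where H02 is genuinely at risk. The second does not depend on that.

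**Working it through.** **Inputs from the documents.** 120 treated, 60 control (Protocol 8.2); one-sided 0.025 for each test, H01 before H02, binomial then Fisher (SAP 7.1.1). The plan's power, expected rates and dropout are not visible, so its sample size cannot be reproduced; only the split can be checked (180 at 2:1 = 120 and 60, which agrees).

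**Assumptions.** Two equal strata (60 treated and 30 control in each); treated mean 60, 65 or 70%; control mean 10-50%; strata 0, 20 or 40 points apart in both arms. All results below are full enumerations of binomial outcomes, except the 15-site check at the end, which is a simulation.

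**Step 1: the H01 gate.** P(X ≥ 72 | n = 120, p = 0.5) = 0.0177 and P(X ≥ 71) = 0.0274, so H01 needs at least 72/120.

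**Step 2: where H02 can fail after that.** At 72/120, Fisher gives p = 0.0151 with 25/60 control responders (reject) and p = 0.0252 with 26/60 (fail). H02 is at risk only if about 43% or more of the untreated controls respond.

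**Step 3: size of Fisher's test.** At common response rates of 5, 10, 20 and 30% it is 0.008, 0.012, 0.015 and 0.017; the maximum is 0.018. With null stratum rates of 10% and 50%, Fisher has size 0.0095 and the exact conditional stratified test 0.0159. Both are valid; the stratified test wastes less of the 0.025.

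**Step 4: gain in passing both tests, exact stratified minus Fisher (percentage points, treated mean 60-70%).**

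| Spread between strata | Control 30% | Control 40% | Control 50% |
|---|---|---|---|
| 20 points | 0.01 to 0.07 | 0.2 to 0.7 | 0.6 to 1.4 |
| 40 points | at most 0.1 | 0.9 to 2.5 | 3.6 to 6.8 |

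With no spread the difference is -0.16 to +0.02 over the whole grid. At control rates of 10-20% it is zero to two decimals.

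**Step 5: separate stratification from loss of exactness.** The asymptotic Cochran-Mantel-Haenszel (CMH) test, without continuity correction, gains more at a 20-point spread: 1.2-2.6 points at 40% control and 3.9-7.1 at 50%. An unstratified pooled z test already gains 0.9-2.0 and 2.9-5.7, so 74-82% of the CMH gain comes from giving up exactness. Stratifying itself adds 0.3-0.6 and 1.0-1.8 points.

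Example, treated 55%/75% vs control 30%/50%: Fisher 81.5%, exact stratified 82.0%, pooled z 83.4%, CMH 84.0%. The CMH test is also not capped at 0.025: its size is 0.0255 at null rates 50%/50% and 0.029 at 85%/95%.

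**Step 6: precision of the risk difference.** SE = sqrt(v_T/120 + v_C/60). Unstratified, v is p(1-p) at the arm's overall rate; stratified, v is the mean of p(1-p) over strata. At 65% vs 20%:

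- Unstratified: sqrt(0.2275/120 + 0.16/60) = 0.0675; 95% half-width 1.96 × 0.0675 = 13.2 points.
- 20-point spread (55/75 vs 10/30): sqrt(0.2175/120 + 0.15/60) = 0.0657; half-width 12.9 points.
- 40-point spread (45/85 vs 0/40): sqrt(0.1875/120 + 0.12/60) = 0.0597; half-width 11.7 points.

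Over the grid, the SE is 2.1-3.9% smaller at 20 points (control 10-50%) and 8.5-12.1% smaller at 40 points (control 20-50%).

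**Step 7: sparse strata.** If all 15 sites were strata (8 treated and 4 control each), simulation with no site effect at 65% vs 40% gave a mean simple stratified SE of 0.068 against an empirical 0.076. That interval would be falsely narrow.

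**The case against.** Nothing in the plan is wrong: Fisher's test controls the error rate, is pre-specified, and is the same in both documents. The gain in trial success lies where nearly half of untreated controls improve, which seems unlikely over 12 weeks when Protocol 8.4.1.1 requires improvement on both jawlines. The gain also fades at higher treated response: with 40% control response and a 20-point spread it is about 0.1 point at 75% treated and 0.01 at 80%. The largest figure, 6.8 points, needs treated strata at 50%/90% and control strata at 30%/70%. The strata are redacted, so their prognostic value is unknown, and the power sentence in Protocol 8.2 is cut off and followed by arm sizes rather than by anything about the H02 test. A supportive stratified estimate would deliver the precision without touching the primary test.

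All of this stands as a limit on importance. It rules out calling the point an error and makes the gain in trial success conditional. It does not remove the case for using strata the trial already pays to balance: the exact version keeps strict error control, the worst loss found is 0.16 points, and the precision gain does not need a high control rate.

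**Conclusion.** The point holds as an optional improvement. Fisher's test is valid, and for control response of 30% or less changing the test makes essentially no difference to trial success. At 40-50% control response and treated means of 60-70%, an exact stratified test adds 0.2-1.4 points at a 20-point spread and 0.9-6.8 points at 40. The precision gain is 2.1-3.9% in standard error at 20 points and 8.5-12.1% at 40.

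These figures assume two equal strata with the same spread in both arms. If the strata do not predict response, there is nothing to gain. Confidence is medium, because the factors, their number and the expected rates are not visible.

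**What to change.** In SAP 7.1.1:

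- Name for H02 a one-sided 0.025 exact conditional Cochran-Mantel-Haenszel test stratified by the randomisation factors.
- State in advance how sparse strata are pooled, and use a sparse-data variance if sites are strata.
- Report the Mantel-Haenszel risk difference with its stratified confidence interval, unless the redacted text already does.
- Keep Fisher's exact test as a sensitivity analysis. Leave H01, its binomial test and the test order unchanged.

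The sponsor knows its strata and can instead record why they are not expected to be prognostic. Either way, settle it before database lock and before any Week 12 results by arm are seen.

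Cost: no extra subjects or data. Protocol 8.4 allows the route: "Deviations from the analyses outlined in this protocol will be documented in the SAP". A SAP-only change would, however, make the SAP's primary test differ from Protocol 8.4.1.1, so the departure must be stated. If the protocol text is edited too, Protocol 9.9 applies: "All protocol modifications require written IEC/IRB approval/favorable opinion", together with submission to the regulatory authority. The asymptotic CMH test is not proposed as the default, because its size can exceed 0.025.

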7.1.2 Secondary Effectiveness Endpoint

[figure not shown]
The secondary effectiveness endpoints analyses will be conducted using the ITT population using OC, i.e. without imputation of missing values. Additionally, summary of the secondary effectiveness endpoints will also be conducted using the PP population, with OC.

[figure not shown]
- For the FACE-Q satisfaction with the lower face and jawline assessment, among treated subjects, sum scores and the equivalent Rasch-transformed scores will be summarized using descriptive statistics [REDACTED]
[REDACTED]
[REDACTED]
[REDACTED].
- The investigator GAIS for treated subjects will be descriptively summarized at Week 12 using counts (n) and percentages (%) for each GAIS category [REDACTED]
[REDACTED]
[REDACTED]
[REDACTED]
[REDACTED].
- The subject-rated GAIS for treated subjects will be descriptively summarized at Week 12 using counts (n) and percentages (%) for each GAIS category [REDACTED]
[REDACTED]
[REDACTED]
[REDACTED]
[REDACTED].
- The proportion of responders in the treatment group and the untreated control group at Week 12, according to the MJAS, [REDACTED]
[REDACTED]
[REDACTED]
[REDACTED].

[figure not shown]
[REDACTED] will be summarized using counts and percentages. Treatment response is defined as \geq 1-point improvement [REDACTED]
[REDACTED]
[REDACTED]
[REDACTED]

[figure not shown]
7.1.3 [REDACTED]

[figure not shown]

[figure not shown]

7.2 Safety Endpoints

All safety analyses will be performed on the SES. AEs will be coded according to the Medical Dictionary for Regulatory Activities (MedDRA). The version of MedDRA used will be documented in the data management plan (DMP).

[figure not shown]
Only treatment emergent adverse events (TEAEs) will be analyzed. [REDACTED]

[figure not shown]
A large rectangular black box redacting content from page 23 of 56.

[figure not shown]
An overall summary of AEs will be provided by treatment group and overall, for the following:

- Any AEs
- Any non-TEAEs
- Any TEAEs
- Any treatment-related TEAEs [REDACTED]
- Any serious TEAEs
- Any TEAEs leading to discontinuation

Listings for all AEs as well as subsets such as TEAEs leading to discontinuation, serious TEAEs, and deaths will be provided.

7.3.4 Previous Medication and Therapy

Previous medications/therapies will be categorized according to the start and stop dates of the medication as:

- Medication/therapies started and stopped prior to the baseline visit will be treated as Previous Medication.
- Medication/therapies started prior to the baseline visit and stopped or ongoing during the study period will be treated as Concomitant Medications.
- Medications/therapies started after the baseline visit will be treated as Concomitant Medication.

Frequencies of concomitant medications will be given based on different ATC code levels as well as by WHO preferred name for the ITT population. Indications for concomitant procedures will be coded and only listed. Where there is insufficient data available to confirm whether a medication/therapy should be classified as previous or concomitant, it will be treated as previous.

7.3.5 Demographic Data

Demographic characteristics [REDACTED] and baseline characteristics [REDACTED] will be presented using standard descriptive statistics for continuous variables (n, mean, SD, median, minimum, and maximum) and for qualitative variables (absolute and percent frequencies (n, %)). Demographic and baseline characteristics will be summarized for the ITT, SES and the PP populations.

The body mass index will be calculated as follows:

$$\text{BMI } [\text{kg}/\text{m}^2] = \text{body weight}[\text{kg}] / (\text{height}[\text{cm}]/100)^2$$

Post-baseline weight will only be listed.

7.3.6 Exposure Data

Subjects' exposure to study product will be summarized for the SES (as exposed to product if different from as randomized for any reason) according to the following:

- (1) Frequencies of subjects receiving initial treatment and touch-up will be summarized by treatment group [REDACTED]
[REDACTED]

(2) Frequency of subjects receiving the optional re-treatment (Week 48) will also be summarized for the baseline treatment group;

[REDACTED]

[figure not shown]
Frequencies of pre- and post-treatment skin applications will be given based on different ATC code levels.

[figure not shown]
Data regarding device malfunction/technical complaint associated with the treatment injections will be listed only.

7.4 Special Statistical/Analytical Issues

7.4.1

[REDACTED]

7.4.2 *Interim Analyses*

No formal interim analysis is planned. [REDACTED]

[figure not shown]
[REDACTED] The annual reports generally may require enrollment updates (i.e., number of subjects screened and enrolled (overall and by site), numbers randomized, etc.), subject disposition, and safety listing.

7.4.3

[REDACTED]

8 [REDACTED]

[REDACTED]

